**10.2.16 Extension Study - Visit 14, Day 295 (+/-3) -**

- Perform physical examination (see Section 15.1.3 for details)
- Measure and record vital signs and weight (see Section 15.1.5 for details)
- Draw blood and prepare sample for serum chemistry and hematology
- Collect urine sample for urinalysis (see Section 14.1 for details)
- Record concomitant medications
- Record any SAEs that have occurred since the last visit
- Perform study drug accountability

**10.2.17 Extension Study - Visit 15, Study Day 337 / End of Treatment / Early Discontinuation**

The following procedures will be conducted on Day 337: ( $\pm 7$  days):

- Perform MMSE
- Perform cognitive testing and functional assessments (see Section 16)
- Administer C-SSRS (see Section 16.1 for details)
- Perform physical examination (see Section 15.1.3 for details)
- Measure and record vital signs and weight (see Section 15.1.5 for details)
- Perform 12-lead ECG (see Section 15.1.6 for details)
- Draw blood and prepare sample for serum chemistry and hematology (see Section 14.1 for details) as well as for coagulation testing (prothrombin time [PT/INR]).
- Collect urine sample for urinalysis (see Section 14.1 for details)
- Draw blood and prepare samples for PK
- Perform  $^{11}\text{C}$ -UCB-J Imaging
- Perform  $^{18}\text{F}$ -FDG Imaging
- Perform MRI Imaging

- Optional - Perform a lumbar puncture and collect CSF samples for PK and PD analyses
- Record concomitant medications
- Record any SAEs that have occurred since the last visit
- Administer final dose of study drug
- Perform study drug accountability

#### **10.2.18 Extension Study - Visit 16 / Day 352**

- Physical examination
- ECG
- Vital signs, weight
- Hematology, biochemistry
- Urinalysis

### **10.3 Concomitant Medications and Other Restrictions**

All medications mentioned in the exclusion criteria (Section 9.3) are expressly prohibited at any time during the study. Exceptions to the list of excluded medications may be made on a case-by-case basis if discussed and approved by the medical monitor in advance. Intake of drugs or substances potentially involved in clinically significant CYP3A4 or P-gp mediated drug interactions with CT1812, within 4 weeks or five half-lives of the interacting drug prior to administration of CT1812 and throughout the course of the study. Grapefruit juice should be avoided in the two weeks prior to dosing. See Appendix A for a list of these prohibited substances.

Participants may be on stable doses (at least 30 days prior to screening) of an acetylcholinesterase inhibitor and/or memantine and continue these medications during the study. Participants may be on a stable dose (at least 60 days prior to screening) of a selective serotonin reuptake inhibitor antidepressant and may continue this medication during the study.

## **11 CSF COLLECTION ASSESSMENTS**

### **11.1 Lumbar Puncture**

Each participant will undergo a lumbar puncture as part of the screening process and with the Day 169 visit. Lumbar punctures will be performed by study physicians specifically trained in the

procedure. Prior to the LP, a coagulation panel will be obtained to rule out a clotting disorder. Participants will be excluded from having an LP if he or she has an allergy to all local anesthetics (such as lidocaine) and/or has any medical condition requiring treatment with warfarin or heparin. The investigator may choose to have the lumbar puncture performed with the help of fluoroscopy. Lumbar punctures performed with the help of x-rays will be done at Yale-New Haven Hospital. Obtained CSF should be sent for cell counts (white blood cells and red blood cells, with differential if either of the counts is abnormal), CSF protein, and CSF glucose.

Approximately 15 mL of CSF will be collected at each lumbar puncture.

### ***11.2 Timing of CSF Collections***

At baseline and Day 169, CSF will be collected prior to the administration of the study drug dose due on that study day.

### ***11.3 Volume of CSF Collected***

The total volume of CSF collected from each participant during this study will be approximately 30 mL.

### ***11.4 Handling, Shipping, Storage and Analysis of CSF***

Refer to the Laboratory Procedures Manual for the handling of CSF samples. Participant CSF specimens collected during this study may be stored for up to 15 years and used to further the knowledge of CT1812.

## **12 PET IMAGING**

Participants will have two F-FDG, three C-UCB-J scans, and one C-PiB scan as part of their research participation.

PET scans are acquired as participants lie supine on the scanner bed. Venous catheters will be used for intravenous administration of the radiotracer. PET scans will be performed with the Siemens HRRT. An attenuation correction scan is obtained immediately before or after each emission scan. For each PET scan with C-UCB-J, up to 20 mCi will be administered by infusion pump, followed by dynamic PET data acquisition. Maximum mass dose from the radioligand will be limited to ≤3.25 µg to minimize any self-occupancy. For C-PiB, the maximum dose is 15 mCi and for F-FDG, the maximum dose is 5 mCi of F-FDG. For each of these, the scan extends

for up to 90 min. Vital signs (blood pressure, pulse and respiration) are collected prior to and during each PET scan. The participants will have fasted for at least 4 h prior to the F-FDG scan. Participants with history of prior radiation exposure for research purposes or exposure to workplace radiation within the past year such that participation in this study would place them over the FDA limits for annual radiation exposure will be excluded from participating in this study. If a positive result is received, study participation will be cancelled.

### 13 MAGNETIC RESONANCE IMAGING (MRI)

Participants will have a brain MRI scan as part of the screening evaluation. MRI scans will take place at [REDACTED]. Participants that have any contraindications for MRI studies, including claustrophobia, the presence of metal (ferromagnetic) implants, or cardiac pacemaker will be excluded from participating in this the study.

The MRI will be performed using either [REDACTED]. The MRI will ensure that patients do not meet exclusion criteria by showing evidence of infection, infarction, or other focal brain lesions. Participants with multiple lacunes, or lacunes in a critical memory structure, will also be excluded. The MRI will take approximately 30 minutes to complete. We will not use sedation or MRI with contrast.

Every time an MRI is acquired, the following MRI acquisition sequence will be acquired using a [REDACTED]

[REDACTED]

- [REDACTED]
- [REDACTED]
- [REDACTED]
- [REDACTED]
- [REDACTED]
- [REDACTED]
- [REDACTED]

## **14 BLOOD AND URINE COLLECTION**

### ***14.1 Clinical Laboratory Testing***

Hematology testing will include red blood cell count, erythrocyte mean corpuscular hemoglobin concentration (MCHC), erythrocyte mean corpuscular volume (MCV), hematocrit, hemoglobin, leukocyte count, and absolute counts of monocytes, neutrophils, basophils, eosinophils and platelets.

Serum chemistry analyses will include glucose, calcium, albumin, total protein, sodium, potassium, bicarbonate, chloride, magnesium, BUN, creatinine, creatine kinase, alkaline phosphatase, ALT, AST, bilirubin, lipase, lactate dehydrogenase (LDH) and phosphorus.

Urinalysis will include osmolality, creatinine, calcium, sodium, turbidity, color, specific gravity, pH, protein, glucose, ketones, bilirubin, blood, urobilinogen, nitrite, leukocytes, and microscopic particles. Urine should not be first morning void. Microscopic examination will be performed if urinalysis results are abnormal for bacteria, casts, epithelial cells, erythrocytes or leukocytes. Urine should be collected within two hours of blood draws for hematology and chemistry panels. Should not be first morning urine. Trace protein will be considered positive.

### ***14.2 Screening Laboratory Tests***

The following will be performed only at screening to confirm participant eligibility:

- Viral serology: hepatitis B antigen, anti-hepatitis C antibody and anti-HIV antibodies.
- Coagulation testing (prothrombin time [PT/INR]). Coagulation testing may be repeated if medically indicated or if required by local practice.
- Thyroid panel, B12 and folate

### ***14.3 Blood Sample collection of Pharmacokinetic and Pharmacodynamic Analyses***

#### **14.3.1 Timing of Blood Sample Collection**

- On clinic visit days, blood samples for the measurement of plasma CT1812 levels and proteomics will be drawn prior to administration of study drug due for that day.

#### **14.4 Volume of Blood Collected**

A total of approximately 123 mL of blood will be collected during the screen and Primary study period and approximately 120 mL blood will be collected during the Extension study. Refer to the study laboratory manual for required blood draw volumes for each test at all time points.

#### **14.5 Handling, Shipping, Storage and Analysis of Plasma**

Please refer to the Laboratory Procedures Manual for the handling of blood and plasma samples. Participant plasma specimens collected during this study may be stored for up to 15 years and used to further the knowledge of CT1812.

### **15 SAFETY ASSESSMENTS**

#### **15.1 Assessment of Safety**

##### **15.1.1 Safety Oversight**

A study safety monitoring committee will oversee the safety of the trial. This committee will include the study director, the study medical monitor and the study principal investigator. Safety data (lab reports, AEs) will be provided to the safety committee to review at bi-weekly intervals during the trial and the committee will at minimum, meet once quarterly to discuss trial safety data.

##### **15.1.2 Adverse Events**

Adverse events will be captured from the start of study-related procedures at Visit 1 (including diagnostic assessments or signing of the Informed Consent Form [ICF]) onward during the course of this study. Important medical events and conditions occurring prior to this period are not AEs; they will be captured within the medical chart and in the Medical History section of the Case Report Form.

##### **15.1.3 Physical and Neurological Examination**

The investigator should perform a thorough examination of all body systems (exception: genitourinary and reproductive should be symptom-directed). The neurological exam is symptom-directed and may include mental state, speech, gait/posture, arm swinging, facial movements, tongue, muscle wasting (power and tone), coordination, reflexes, and sensation.

Height should be measured at Screening only. For body weight measurements, the Investigator must ensure that the scale is properly calibrated prior to study initiation, and that the same scale is used throughout the study. Weight will be collected at each visit.

#### **15.1.4 Medical, Surgical and Psychiatric History**

Medical, surgical and psychiatric history including a current DSM-V diagnosis that would interfere with the participant's ability to participate in the study including any prior history of suicidal thoughts or behavior that are believed by the investigator to represent a current safety risk (see section 14.1.12.1).

#### **15.1.5 Vital Signs**

Vital signs include body temperature, systolic and diastolic blood pressure, pulse rate and respiration rate. Body temperature will only be recorded once daily. Blood pressure and pulse rate recordings will be made after the study patient has been sitting or semi-supine and at rest for  $\geq 5$  minutes.

#### **15.1.6 12-lead Electrocardiogram**

ECGs will be recorded using a digital ECG to provide machine-generated interval measurements. The Bazett formula should be utilized for QTc interval correction:

$$QT_c = \frac{QT}{\sqrt{RR}}$$

## **15.2 Adverse Events**

### **15.2.1 Definitions**

#### **Adverse Event**

An AE is any untoward medical occurrence in a participant or clinical investigation participant undergoing a study procedure or administration of a study drug. An AE can therefore be any unfavorable and unintended sign (including an abnormal laboratory finding), symptom, or disease temporally associated with the use of the study drug, whether or not considered related to the study drug.

#### **Related Adverse Event**

A related AE is an AE with a causality rating of possible" or "probable".

### **Unrelated Adverse Event**

An unrelated AE is an AE with a causality rating of “unlikely” or “unrelated”.

### **Laboratory Abnormality**

A laboratory abnormality is any clinically significant laboratory abnormality suggesting a disease or organ toxicity and which is of a severity requiring active management (i.e., changes of dose, discontinuation of drug, more frequent follow-up, medical treatment or a diagnostic investigation). Laboratory abnormalities are also considered AEs, if clinically significant.

### **Pretreatment Adverse Events**

A pretreatment AE is any AE occurring during the pretreatment period (between informed consent and initiation of a study drug).

### **Post-study Adverse Event**

A post-study AE is an AE occurring up to 30 days after the treatment period.

### **Treatment-emergent Adverse Events**

Treatment-emergent adverse events (TEAEs) are all AEs occurring during the treatment period or a pretreatment AE that worsens in intensity during the treatment period.

### **Treatment Period**

The treatment period is the period during which a participant receives study drug (i.e., day of dosing).

### **Serious Adverse Event**

A SAE is any untoward medical occurrence that results in death, is life-threatening, requires in-patient hospitalization or prolongation of existing hospitalization, results in persistent or significant disability/incapacity, is a congenital anomaly/birth defect observed in any offspring of the participant conceived during treatment with the study drug or is an important medical event. See Section 13,3 for more details on SAEs.

## **15.2.2 Collection and Rating of Adverse Events**

During the course of the study (i.e., from the signing of the ICF through the Follow-up Visit plus 30 days for any SAE) all AEs, irrespective of the relatedness to the study drug, will be collected and reported on the Adverse Event Report Form. The seriousness criteria should not be confused

with the intensity of the event. In case of an SAE, a Serious Adverse Event Report Form must be completed and transmitted to the Sponsor or designee.

Overdoses and medication errors in the presence of clinical consequences should be recorded as AEs. The clinical consequence should be reported as “[enter AE] due to overdose”.

#### 15.2.2.1 Onset Date

The onset date is the date when the first sign(s) or symptom(s) were first noted. For example, if the AE is an abnormal laboratory test (such as “platelets low”), the onset date is the date when the sample was taken. If the participant was hospitalized for meningitis, and symptoms such as fever, headache and nausea started the day before the hospitalization, the onset date is the day symptoms presented versus day of hospitalization.

#### 15.2.2.2 Assessment of Intensity

The intensity of each AE will be rated according to the following 3-point scale:

- **Mild:** Awareness of signs or symptoms, but no disruption of usual activity
- **Moderate:** Event sufficient to affect usual activity (disturbing)
- **Severe:** Inability to work or perform usual activities (unacceptable)

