## **4.2 Nonclinical Experience**

### **4.2.1 Nonclinical Pharmacology Studies**

CT1812 is a lipophilic isoindoline formulated as a fumarate salt, and is the result of a structure-based medicinal chemistry optimization program comprised of over 300 analogs. CT1812's properties are fully described along with all preclinical studies in the Investigator Brochure. CT1812 has a high affinity at the target receptor sigma-2/PGRMC1 (S2), and is >100-fold selective for this receptor over other receptors and ion channels. Dose-limiting toxicities at higher doses in both species appear to be hypercalcemia and renal tubular damage, both of which are non-invasively monitored via measurement of serum calcium and urinary markers of renal tubular injury such as kidney injury molecule 1 (KIM-149,50).

*In vitro* pharmacodynamic (PD) studies confirmed CT1812 target binding specificity, affinity and engagement, including the prevention and reversal of A $\beta$  oligomer binding and the prevention of A $\beta$  oligomer-induced synapse loss.

*In vivo* PD studies confirmed the desired consequences of target engagement, including cognitive improvements in an aged transgenic mouse model of AD following oral administration of an apparently tolerated dose of CT1812 daily for 9 weeks. Additional *in vivo* PD studies, using an A $\beta$  oligomer detecting microelectrode in an aged transgenic mouse model of AD, demonstrated that administration of CT1812 caused an acute increase in soluble A $\beta$  oligomers in the interstitial fluid of the hippocampus and a sustained increase in soluble A $\beta$  oligomers in the CSF of the lateral ventricle of the brain. These increases in soluble A $\beta$  oligomers occurred without a change in the amount of soluble A $\beta$  1-40, indicating that displacement of A $\beta$  oligomers occurred following treatment with CT1812.

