#### **7.3.1 Safety Stopping Rules**

The occurrence of any one of the following events will result in suspension of administration of study drug in all participants until safety information can be further reviewed by the Sponsor and Medical Monitor.

- Two occurrences of the same or similar SAE assessed as probably or possibly related to dosing with investigational product
- Two or more different participants with the same or similar severe AE assessed as probably or possibly related to dosing with the investigational product
- Four or more participants with the same or similar moderate AE which is possibly or probably related to dosing with investigational product

Under these circumstances, the Sponsor and Medical Monitor will review the available safety data and, in consultation with the study principal investigator, recommend whether dosing should continue, or if study drug administration should be terminated or dose reduced, or if additional monitoring procedures or safety precautions need to be employed.

If a stopping rule is achieved, selective unblinding of the participants involved may be performed by the Sponsor to determine if the SAEs/AEs are isolated to a single dose group or if they occurred in placebo participants.

The study or a dose group may also be terminated if the Medical Monitor, Study Director and Sponsor, in consultation with the lead principal investigator, determine that any adverse event(s) are occurring that are intolerable or pose a medically unacceptable safety risk.

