#### **FOR INDIVIDUAL PARTICIPANTS:**

Participants who develop a severe adverse event or laboratory abnormality will not receive any additional doses and will be monitored until resolution of the AE or the return of laboratory abnormality to the acceptable screening value(s). Study drug may be re-initiated after consultation with medical monitor and sponsor. Any participant with:

- elevated ALT or AST greater than 5 X ULN should have dosing with study drug stopped and have laboratory tests repeated every 3-4 days until levels return to less than or equal to 1.5 X ULN. If the medical monitor and investigator are in agreement, study drug may be continued while a confirmatory ALT/AST is obtained within 3 days. If the confirmatory ALT/AST tests are below 5 X ULN, study drug may be continued. The frequency of the laboratory tests may be modified after discussion with the medical monitor if the liver enzymes are in a decreasing trend.
- Elevated ALT or AST greater than 3 X ULN in combination with total bilirubin > 2 X ULN or INR > 1.5 X ULN OR an ALT or AST > 3 X ULN with the appearance of fatigue, nausea, vomiting, right upper quadrant pain or tenderness, fever, rash, and/or eosinophilia (>5%) should have dosing with study drug stopped and have laboratory testing repeated every 3-4 days. If the medical monitor and investigator are in agreement, study drug may be continued while a confirmatory laboratory testing is obtained within 3 days. If these criteria are no longer met, study drug can be continued at the discretion of the medical monitor and investigator. The frequency of the laboratory tests may be modified after discussion with the medical monitor if the laboratory tests are trending towards normal.
- An increase in serum creatinine by 0.3 mg/dL (24.4 micromol/L) or 150% of baseline that is without clinical explanation of another etiology will result in repeated serum chemistry testing within 3-7 days. If the serum creatinine elevation is confirmed on repeated testing the study drug will be discontinued. If the serum creatinine elevation resolves upon

subsequent testing after study drug is discontinued the study drug may be restarted with serum creatinine monitoring at the discretion of the medical monitor and investigator.

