- An increase in serum calcium to  $\geq 10.5$  mg/dL (2.63 mmol/L) that is without clinical explanation of another etiology will result in repeated serum chemistry testing within 3-7 days. If the serum calcium elevation is confirmed on repeated testing the study drug will be discontinued. If the serum calcium elevation resolves upon subsequent testing after study drug is discontinued the study drug may be restarted with serum calcium monitoring at the discretion of the medical monitor and investigator.
- Note: Fractional excretion of calcium will be monitored in each participant and interpreted in conjunction with serum creatinine and serum calcium. Given the ability of fractional excretion to fluctuate, no upper limit for discontinuing study drug based on fractional excretion of calcium has been set but it may be used as a stopping rule if persistent unexplained increases in fractional excretion of calcium are observed.

**Note:** Any unanticipated SAEs that are ‘related’ should be reported to the National Institute on Aging within 48 hours of knowledge of the same.

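### A symptom-free laboratory AE that stops a participant's drug has no written basis for a moderate or severe rating, so read literally it misses two study-level stopping rules and SAP Table 14.3.1.5

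*Protocol*

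**What the plan says.** Protocol 15.2.2.2 applies one three-level scale to all AEs. Mild is "Awareness of signs or symptoms, but no disruption of usual activity". Moderate requires that usual activity is affected; severe requires inability to carry it out. The definitions in 15.2.1 bring laboratory findings in: "Laboratory abnormalities are also considered AEs, if clinically significant". The same definition lists drug discontinuation among the forms of active management that identify such an abnormality, so a value that stops drug falls within it.

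Section 7.3.1 has two layers:

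- **Individual stops** are set by laboratory value: ALT/AST above 5 x ULN; ALT/AST above 3 x ULN with raised bilirubin or INR, or with symptoms; and a creatinine or calcium rise with no other explanation. Most depend on a repeat test. For liver enzymes, "If the confirmatory ALT/AST tests are below 5 X ULN, study drug may be continued"; for calcium, "If the serum calcium elevation is confirmed on repeated testing the study drug will be discontinued".
- **Study-level rules** suspend dosing for everyone pending review. One is triggered by two related SAEs. The other two depend on intensity: "Two or more different participants with the same or similar severe AE assessed as probably or possibly related to dosing with the investigational product" and "Four or more participants with the same or similar moderate AE which is possibly or probably related to dosing with investigational product". The synopsis repeats all three.

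SAP Appendix 2 plans Table 14.3.1.5, restricted to treatment-emergent AEs that are related and at least moderate. Protocol 4.2.1 states what the animal studies found: "Dose-limiting toxicities at higher doses in both species appear to be hypercalcemia and renal tubular damage".

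**The concern.** The expected toxicities are ones that laboratory values detect, often before the participant notices anything. The protocol treats such a value as reason to stop dosing in that person, yet its intensity scale has no language for it. The authors did think of laboratory AEs in this part of the protocol, because 15.2.2.1 explains how to date the onset of one; intensity has no matching rule.

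Two things are at stake. The first is pooling across participants: the individual stops act one person at a time, and the rules that would notice several people with the same problem depend on intensity or seriousness. The second is the table a reader would open first to see related events that matter, which filters on the same rating. Incidence and severity of AEs is the first listed component of the primary endpoint (Protocol 6.2.1).

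**Working it through.** **Step 1: trace the event through the text.** Take a participant with no symptoms and a confirmed calcium of 10.5 mg/dL or more, judged possibly related.

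| Question | Where | Answer |
|---|---|---|
| Is it an AE? | Protocol 15.2.1 | Yes, if clinically significant |
| Is drug stopped? | Protocol 7.3.1, individual | Yes, on the confirmed value |
| Is it severe? | Protocol 15.2.2.2 | No, activity is not prevented |
| Is it moderate? | Protocol 15.2.2.2 | No, activity is not affected |
| Does it count toward the two-severe rule? | Protocol 7.3.1, study level | No |
| Does it count toward the four-moderate rule? | Protocol 7.3.1, study level | No |
| Does it count toward the related-SAE rule? | Protocol 7.3.1 and 15.3.1 | Only if judged serious, for example as an important medical event |
| Is it in Table 14.3.1.5? | SAP Appendix 2 | No |

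The same holds for a silent ALT/AST above 5 x ULN and for a confirmed creatinine rise. The zero contribution to the two intensity rules follows from reading the definitions literally; it is not an estimate.

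**Step 2: size.** The documents give no rate for these events, so the rate is assumed.

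- n = 14 active participants (7 + 7, Protocol 17.2).
- p = assumed chance per active participant of one related, symptom-free, drug-stopping event type.
- Formulas: P(X ≥ 1) = 1 − (1 − p)^14, and P(X ≥ 4) = 1 − Σ C(14,k) p^k (1 − p)^(14−k) for k = 0 to 3.

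At p = 0.05, P(X ≥ 1) = 1 − 0.95^14 = 1 − 0.4877 = 0.5123, and P(X ≥ 4) = 1 − (0.4877 + 0.3593 + 0.1229 + 0.0259) = 0.0042.

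| Assumed p | Expected events (14p) | P(X ≥ 1): at least one in the gap | P(X ≥ 4): four-participant rule, if counted |
|---|---|---|---|
| 2% | 0.28 | 0.25 | 0.0001 |
| 5% | 0.70 | 0.51 | 0.004 |
| 7.1% | 1.00 | 0.65 | 0.015 |
| 10% | 1.40 | 0.77 | 0.044 |

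The 7.1% row is 1/14, an illustration only. Protocol 4.3 reports one ALT rise of 4.7 x ULN at 560 mg among 19 patients randomised 1:1:1:1, of whom about 14 were active (19 × 3/4 = 14.25). That rise was below the 5 x ULN limit, and the protocol does not say whether it was symptom-free.

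**Step 3: sensitivity.** Attribution is made blind, so placebo events can count too. Adding 7 placebo participants at an assumed 2%, all judged related, raises P(X ≥ 4) to 0.0086 at 5% and 0.0613 at 10%.

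**The case against.** The best reply is that the text is silent rather than wrong. A silent laboratory value does not match the mild definition exactly either, since that speaks of awareness. Protocol 17.4 leaves severity to the investigator, and 7.3.1 says "Participants who develop a severe adverse event or laboratory abnormality will not receive any additional doses", which can be read as recognising severe laboratory findings. This stands in part: mild is the nearest fit, not an exact one, and an investigator may in practice rate higher. But 15.2.2.2 says how to rate, and nothing written supports a higher grade, so ratings may depend on the rater.

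A reader might infer that these events are lost to follow-up, because note 11 to the schedules extends follow-up only for related AEs of moderate or severe intensity. The documents do not support that. Section 7.3.1 monitors until the value returns to the acceptable screening level, and 15.2.3 follows any AE or clinically significant laboratory value whatever its intensity.

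A reader might also infer that the events become invisible. They do not. They remain in Tables 14.3.1.1, 14.3.1.2 and 14.3.1.4, clinically significant results are profiled in Table 14.3.4.8, and dosing is listed and exposure summarised (SAP 7.1). Laboratory change is itself a listed primary-endpoint component. A temporary stop with restart is harder to pick out, because the action-taken categories include no interruption and Table 14.3.2.2 covers study withdrawal only, but the dosing listing is still there.

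A third tempting reading is that the two-severe rule is being badly disabled. With 14 active participants and rates of 10-20%, two or more events would occur with probability 0.42-0.80. That supposes every drug-stopping value is severe, which nothing in the plan says and which the fix below does not do.

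Finally, the protocol keeps seriousness, intensity and action taken apart, and the creatinine and calcium limits are precautionary. That is a sound argument against grading an event moderate merely because drug was stopped, and the fix respects it.

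**Conclusion.** The gap is real but modest. No written definition lets a symptom-free, drug-stopping laboratory AE be moderate or severe, so read literally two of the three study-level rules and Table 14.3.1.5 do not take it in. Individual numeric stops, the related-SAE rule, biweekly review of laboratory data by the safety committee (15.1.1), discretionary termination and the remaining outputs all continue to work.

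The likelier consequence is omission from Table 14.3.1.5. A missed four-participant trigger is improbable in a trial this small. The figures rest on assumed rates, one event type, independent participants, and every event being related and symptom-free. The safety committee's charter is cited in the SAP but is not among the documents, so a laboratory rule there cannot be excluded. This is a cheap improvement to a safety-first trial, not a defect that undermines its safety conclusions.

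**What to change.** 1. Add to Protocol 7.3.1 and to the synopsis: *A laboratory AE judged possibly or probably related, for which study drug is stopped under an individual ALT/AST, creatinine or calcium criterion after any confirmatory test this section allows, counts toward the four-participant rule whatever its intensity rating.*
2. Add to SAP 8.2 that these events are also shown in Table 14.3.1.5, flagged as laboratory drug-stopping events.

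The scale in 15.2.2.2 can stay as it is. A liver-enzyme spike that falls below the limit on repeat, with dosing continued, is not affected.

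Cost: one sentence in two places and one line in the SAP, using existing limits and data. Dosing may be paused for review slightly more often, an added chance of about 0.004-0.04 at assumed rates of 5-10% in 14 active participants. Table 14.3.1.5 would have a mixed basis for entry, which the flag makes plain.
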